9.3 Clinical Laboratory Determination

Clinical safety laboratory assessments will include tests from the serum chemistry, hematology, and coagulation categories. Where applicable, laboratory values will be graded according to the NCI-CTCAE v5.0.

Local laboratories will be used to determine eligibility or when clinically needed; however, for the safety analysis of laboratory assessments, only laboratory values evaluated at a central laboratory will be used. Unless otherwise specified, all the summaries of the laboratory tests will be presented by the Double-blind period, OLE period, and entire study.

Shift tables of Baseline CTCAE grade to worst post-baseline CTCAE grade will be presented separately for gradable Hematology Parameters and Serum Chemistry Parameters. In the case of bi-directional toxicities, parameters will be presented separately (eg Calcium High, Calcium Low). For the purposes of tabulation, laboratory values which are not assigned NCI-CTCAE Grades 1, 2, 3, or 4 due to a toxicity will be assigned Grade 0 (within the normal range).

All laboratory data (including Hematology parameters, Chemistry parameters, Coagulation parameters, and pregnancy tests) will be included in separate laboratory listings.

A separate summary table for liver tests (ALT, AST, Alkaline Phosphatase, Direct Bilirubin, and Total Bilirubin) will be created. This table will indicate the number and percentage of subjects (presented by lab test) who have a highest post-baseline lab value for the test that is CTCAE Grades 1, 2, 3, or 4.

Observed values and changes from baseline for continuous Hematology and Serum Chemistry laboratory tests will be presented over time in box plots. Reference lines for the LLN and ULN will be included in the plots.

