4.1 Study Period and Visit Window Definitions

4.1.1 Study Periods

The study periods are defined as follows:

Screening Period: Starting the day of signature of informed consent up to and including the day before randomization. For subjects who are not randomized, the screening period will end on the day the subject is determined to be a screen failure.

Double-Blind Period: Starting the day of randomization up to and including the day before the start of chemotherapy in Cycle X + 2.

Observational Period: Starting the first day of chemotherapy in Cycle X + 2 up to and including the day before the pre-chemotherapy IP administration of Cycle X + 3 (if entering the OLE period) or the day of the Follow-Up visit (if not entering the OLE period).

OLE Period: Starting the first day of the pre-chemotherapy IP administration of Cycle X + 3 up to and including the day of the Follow-Up visit in the OLE Period.

Long-Term Follow-Up Period (LTFU): Starting the day after the Follow-Up visit, up to and including a period of 5 years or death, whichever occurs first.

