4.4 Treatment Groups

Data displays for the Double-Blind Treatment period/Observational period will have columns for avatrombopag 60 mg dose and placebo groups, unless otherwise specified. Data displays for the optional OLE period will have 3 columns: subjects randomized to avatrombopag 60 mg dose, subjects randomized to placebo, and a total column (all subjects in the optional OLE period receive avatrombopag 60 mg). Data displays for the entire study will include subjects randomized to avatrombopag 60 mg only.

Data listings will generally include Subject ID, Age/Sex/Race, and an indicator of whether the applicable record occurred during the Screening, Double-Blind, Observational, or OLE periods.

5. Study Patients

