9.4 Other Safety Measures

9.4.1 Vital Signs

By-visit summary tables will be created displaying the observed values and changes from baseline for vital sign parameters, separately for the Double-Blind/Observational period and the OLE period.

A listing of all vital signs entered in the eCRF will also be provided.

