Appendix A: Time and Events Schedule

Table 1. Schedule of Procedures (Double-Blind Treatment Period)

Day	Chemotherapy Cycle X ^a			Chemotherapy Cycle X + 1		
	Screening D -28 to D -1	Baseline	Pre-Chemo IP Treatment (5D)	Chemo Day (D1 up to D3)	Post-Chemo IP Treatment (5D)	D11 (±1D), D15 (±1D), and D18 (±1D)
Visit	1 ^b	2	3 ^c	4 ^d	5 ^e	6, 7, 8
Subject informed consent	X					
I/E criteria	X	X				
Randomization		X ^f				
Demographics (incl. race)	X					
Medical history ^g	X					
ECOG performance status	X					
Concomitant medications ^h	X	X	X	X	X	X
Adverse events	X	X	X	X	X	X
Physical examination	X	X ⁱ		X ⁱ		
Vital signs ^j	X	X		X		
PK ^k			X		X	
Hematology (incl. platelet counts) ^l	X ^b	X	X	X	X	X
Coagulation panel (central lab)		X			X	
Serum chemistry ^m	X ^b	X		X	X	
Pregnancy testing ⁿ	X ^b	X ^o				
Bleeding assessment (ISTH)		← continuous → ^p				
Contact IRT	X	X	X		X	
IP dosing ^q		X	X ^r		X ^r	
Dispense IP and dosing diary		X		X ^s		
Collect dosing diary and IP package			X		X	

Chemo = chemotherapy; D = day(s); ECOG = Eastern Cooperative Oncology Group; I/E = inclusion/exclusion; incl. = including; IP = investigational product; IRT = Interactive Response Technology; ISTH = International Society on Thrombosis and Haemostasis; PK = pharmacokinetic.

Note: Prior to conducting any study-related activities, written informed consent must be signed and dated by the subject. Throughout the double-blind treatment period, all subjects will be assessed for platelet transfusions and chemotherapy dose reductions or delays.

a. The qualifying chemo cycle is defined as Cycle X.

Confidential

- b. Screening Visit may occur on the same day as the Baseline Visit, if one day prior to IP treatment. If these visits occur on the same day, only the Baseline (Visit 2) laboratory samples should be sent to the central lab. Local platelet counts may be repeated as needed.
- c. Visit 3 will occur on the last day of the 5-day pre-chemo IP treatment.
- d. Chemotherapy Day may be 1 to 3 days depending on the subject's chemotherapy regimen (eg, if chemotherapy is given on Day 1 and Day 2, subjects will receive avatrombopag or placebo on Day 3). Avatrombopag or placebo will not be administered concurrently with chemotherapy on Chemotherapy Day. All assessments will occur on the first day of chemotherapy prior to chemotherapy dosing.
- e. Visit 5 will occur on the last day of the 5-day post-chemo IP treatment.
- f. Randomization must occur prior to IP dosing.

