- g. Medical history to include tumor type, date of cancer diagnosis, and prior chemotherapeutic regimens (numbers of cycles, dates).
- h. Concomitant medications to include details of chemotherapeutic regimen (doses, schedule)
- i. Symptom-directed physical examination; full physical examination only required at Screening.
- j. Includes height (at the Screening Visit only), weight (Screening and Baseline Visits only), body temperature (Screening and Baseline Visits only), blood pressure, and pulse rate, and will be measured after resting for 5 minutes. Only screening vital signs will be recorded if screening and baseline visits occur the same day.
- k. Blood samples for PK analysis will be collected at the following time points: pre-dose and 0.5-2, 2-4, and 4-6 hours post-dose. A pre-dose PK sample will be collected within 30 minutes of IP dosing. Each PK sample must be separated by at least one hour from adjacent samples. Pharmacokinetic samples do not need to be collected at identical times for pre- and post-chemo visits.
- l. Hematology samples should be sent to the central lab at Visits 1, 2, 3, 4, and 5. Platelet counts at Baseline (Visit 2) may be performed prior (-1 day) to randomization. Only local lab platelet counts will be assessed at Visits 6, 7, and 8.
- m. Screening chemistries can be performed locally to determine eligibility. Chemistry samples will be sent to the central lab at Visits 1, 2, 4, and 5.
- n. For females of childbearing potential only. A serum or urine pregnancy test will be performed at the Screening Visit. At the Baseline Visit, the pregnancy test will be performed prior to IP administration.
- o. Urine or serum pregnancy test will be performed at the Baseline Visit.
- p. Assessment of bleeding will be performed if a subject has an unscheduled study visit.

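### SAP 9.3 cuts laboratory summaries at the Double-Blind Period, while other safety summaries use Double-Blind/Observational; read literally, the placebo comparison loses Visit 9 and the non-OLE Visit 17

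*SAP*

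**What the plan says.** SAP 9.3 plans CTCAE shift tables, a liver-test table and box plots over time. Its period rule, which yields to anything specified elsewhere, is that "all the summaries of the laboratory tests will be presented by the Double-blind period, OLE period, and entire study".

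SAP 4.1.1 defines the Double-Blind Period as "Starting the day of randomization up to and including the day before the start of chemotherapy in Cycle X + 2". The Observational Period is the next one: "Starting the first day of chemotherapy in Cycle X + 2 up to and including the day before the pre-chemotherapy IP administration" of Cycle X+3, or the day of the Follow-Up visit for subjects who do not enter the OLE. SAP 4.4 adds: "Data displays for the entire study will include subjects randomized to avatrombopag 60 mg only".

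The other safety sections use a different label. Vital signs (SAP 9.4.1) are summarised "separately for the Double-Blind/Observational period and the OLE period". Adverse events (9.2), ISTH bleeding (9.4.2) and transfusions (9.4.3) use the same combined period. The baseline rule in 4.3.4 and the avatrombopag and placebo columns in 4.4 are also written for the combined display.

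SAP 4.1.2 has its own rule for worst-grade shift tables and liver tests: every post-baseline value counts.

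On sampling, SAP Appendix A, Table 1 states: "Chemistry samples will be sent to the central lab at Visits 1, 2, 4, and 5", "Visit 5 will occur on the last day of the 5-day post-chemo IP treatment" and "Only local lab platelet counts will be assessed at Visits 6, 7, and 8". Table 2 marks central chemistry and hematology at Visits 9 and 17. Visit 9 assessments are made on the first day of Cycle X+2 chemotherapy, before it is given.

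**The concern.** Laboratory data are the one by-arm safety outcome reported over the shorter period. The cut falls one day before the first routinely scheduled central sample taken after dosing has stopped. The primary efficacy window in SAP 8.1 runs through Chemotherapy Day of Cycle X+2, so the laboratory window closes before the efficacy window does.

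Safety is a secondary objective, and the double-blind part of the trial gives the only randomised laboratory comparison. A change in liver tests or blood counts that first appears after the last dose could be absent from the two-arm summaries although it was measured in both arms. One group shows this well. Protocol 4.4 bars subjects with liver tests above stated limits from the OLE, so their Visit 17 falls in the Observational Period, which the literal wording of 9.3 leaves out.

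**Working it through.** No figure in the plan needs reproducing. The check places each scheduled central sample in its SAP 4.1.1 period and then does the day count.

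**Step 1: which visits fall where**

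| Visit | Timing | Central chemistry | SAP 4.1.1 period |
|---|---|---|---|
| 4 | Cycle X+1 Day 1, before chemotherapy | yes | Double-Blind |
| 5 | last day of post-chemotherapy IP | yes | Double-Blind |
| 6, 7, 8 | Days 11, 15, 18 | no (local platelet counts only) | Double-Blind |
| 9 | Cycle X+2 Day 1, before chemotherapy | yes | Observational |
| 17, no OLE | Follow-Up | yes | Observational |
| 17, after OLE | Follow-Up | yes | OLE |

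Scheduled post-baseline chemistry through the end of the Observational Period is four visits for subjects not entering the OLE (4, 5, 9, 17), of which two lie outside the Double-Blind Period. For OLE entrants it is three visits (4, 5, 9), of which one lies outside. Central hematology follows the same pattern: Visits 3, 4 and 5 inside, Visits 9 and 17 outside. SAP 4.3.2 uses only central platelet counts for safety, so the local counts at Visits 6 to 8 do not fill the gap.

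**Step 2: how long the gap is**

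Inputs: last day c of Chemotherapy Day is 1, 2 or 3; IP is then taken for 5 days; cycle length L is 21 or 28 days; Cycle X+2 starts on time.

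- Visit 5 = c + 5, which is Day 6 to Day 8.
- Visit 9 = L + 1, which is Day 22 or Day 29.
- The Double-Blind Period ends on Day L.
- Last dose to Visit 9 = (L + 1) - (c + 5). For L = 21: 22 - 8 = 14 to 22 - 6 = 16 days. For L = 28: 29 - 8 = 21 to 29 - 6 = 23 days.
- Double-Blind days after Visit 5 = L - (c + 5). For L = 21: 21 - 8 = 13 to 21 - 6 = 15 days. For L = 28: 28 - 8 = 20 to 28 - 6 = 22 days. No chemistry is scheduled in them.

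**Step 3: Visit 17 without OLE**

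If there is a Cycle X+3, the visit falls 1 to 3 days before its first day, which is Day 2L + 1.

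- L = 21: Days 40 to 42, so 40 - 8 = 32 to 42 - 6 = 36 days after the last dose.
- L = 28: Days 54 to 56, so 54 - 8 = 46 to 56 - 6 = 50 days.

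If Cycle X+2 is the last cycle, the visit is 30 ± 3 days after its Chemotherapy Day. Counting from Cycle X+2 Day 1 with L = 21, that is Days 49 to 55, so 49 - 8 = 41 to 55 - 6 = 49 days after the last dose.

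**Step 4: which displays are affected**

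- Box plots: only 9.3 sets their period. Visits 9 and 17 are outside.
- Shift and liver-test tables: 9.3 cuts at the Double-Blind Period, 4.1.2 counts all post-baseline values, and neither says which prevails.
- Entire-study displays: these contain Visits 9 and 17, but only for subjects randomised to avatrombopag.

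**The case against.** The strongest reply is SAP 4.1.2. It names the two tables that matter most, and 9.3 gives way to anything specified elsewhere, so 4.1.2 can be read as restoring Visits 9 and 17 to them. This stands as a possible reading. The opposite reading is also open: 4.1.2 sits under visit windows, next to a rule on scheduled and unscheduled counts, and may only mean every value within the displayed period. Taken without any period limit, it would put OLE values, measured on open-label avatrombopag, into the placebo column. The SAP does not settle the matter.

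Second, the label may be loose drafting. SAP 9.1 uses the same three headings, yet expects Cycle X+2 chemotherapy counts in one of its tables, and 4.4 defines two-arm columns only for the combined display. That is fair, and it points to the same correction.

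Third, a reader might infer that the Visit 9 and 17 results are dropped altogether, or that no post-dosing chemistry can reach the two-arm tables. The documents do not support either. All laboratory data are listed, and the avatrombopag arm appears in the entire-study displays. The Early Termination visit includes chemistry and can fall inside the Double-Blind Period, as can unscheduled central samples.

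Fourth, under Protocol 9.1 laboratory abnormalities with symptoms or needing intervention become adverse events, and those tables cover the combined period by arm. What could be missed is therefore mainly asymptomatic grade shifts.

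**Conclusion.** The inconsistency is real and worth correcting. On the literal text of 9.3 and 4.1.1, the two-arm laboratory summaries rest on Visits 4 and 5 as the only routinely scheduled post-baseline chemistry. They leave out Visit 9 for everyone and Visit 17 for subjects not entering the OLE. The loss is clear for the box plots and unresolved for the shift and liver-test tables. What is lost is the comparison with placebo, not the data.

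Visit 9 is the more important omission. It is drawn before Cycle X+2 chemotherapy, so it reflects Cycle X+1 alone. Visit 17 also reflects a chemotherapy cycle given without IP, and it falls in the Observational Period only for subjects who did not go on to the OLE.

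The day counts assume on-time cycles and a full post-chemotherapy IP course; a delayed Cycle X+2 lengthens the gap to Visit 9. Nothing in the documents shows that the tables would flatter avatrombopag: adding the visits may raise worst-grade rates slightly in both arms.

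**What to change.** In SAP 9.3, replace Double-blind period with Double-Blind/Observational period for all by-arm laboratory summaries: shift tables, liver-test table and box plots. In SAP 4.1.2, state that the rule on all post-baseline values applies within each displayed period, so that OLE values from placebo-randomised subjects do not enter the placebo column.

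The cost is one phrase in each section and matching table shells. No visit, sample, endpoint or alpha changes. Worst-grade rates may rise slightly in both arms, and Visit 17 values should be read as including the effect of Cycle X+2 chemotherapy.

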9.4 Other Safety Measures

9.4.1 Vital Signs

By-visit summary tables will be created displaying the observed values and changes from baseline for vital sign parameters, separately for the Double-Blind/Observational period and the OLE period.

A listing of all vital signs entered in the eCRF will also be provided.

9.4.2 ISTH Bleeding Information

A tabular summary of ISTH Bleeding Information will be provided and will include the number and percentage of subjects in the Double-Blind/Observational period, OLE period, and entire study who have experienced bleeding in the following categories: any bleeding, major bleeding, non-major clinically relevant bleeding, and minor bleeding.

A data listing of ISTH Bleeding information will also be provided which will include the criteria for major classification, major bleeding at a critical site, and non-major clinically relevant bleeding.

9.4.3 Blood Transfusions

A summary table will be created to display the frequency and percentage of subjects, separately for the Double-Blind/Observational period, OLE period, and

Confidential

entire study who have blood transfusions (yes/no). The type of blood product (Red Blood Cells, Platelets, Cryoprecipitate) will be summarized (subjects may appear in more than one category) and the reason for transfusion (Thrombocytopenia, Bleeding Event, Adverse Event other than Bleeding Event, Other) will be summarized (subjects may appear in more than one category). The total number of packs/units received per transfusion will be summarized as a continuous variable.

Details of any blood product transfusions occurring during the study will be presented in a listing.

9.4.4 ECOG Performance Status

The ECOG performance status will be presented in a listing.

9.4.5 Long Term Follow-Up (LTFU) Period

The number and percentage of subjects who entered (Yes vs No), completed (Yes vs No), and remain ongoing during the 5-year LTFU period will be summarized. The reasons for not entering the LTFU and the reasons for not completing the LTFU period will also be tabulated. The number and percentage of subjects who developed a secondary malignancy (Yes vs No), and the number and percentage of deaths occurring during the LTFU period along with the cause of death (if known) will be tabulated for all subjects who participated in the LTFU period. A data listing, with details of any secondary malignancies reported, will also be provided for all subjects in the LTFU period.

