### 3.1.5 Long-Term Follow-Up Period

After the Follow-Up Visit, all subjects will be contacted approximately every 6 months for up to 5 years by telephone during the Long-Term Follow-Up Period for documentation of vital status (if death occurred, record of date of death) and occurrence of secondary malignancies. If a secondary malignancy has occurred, the following information will be collected: date of onset and type of malignancy, as well as a written narrative from the clinical site summarizing the course of events leading up to diagnosis of the secondary malignancy.

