### 3.2 Study Duration and End of Study

The study will consist of the following periods:

- Double-Blind Treatment Period and Observational Period of approximately 8 to 9 weeks,
- Optional OLE Period until the subject's current chemotherapy regimen changes or the subject completes chemotherapy, and
- Long-Term Follow-Up Period of up to 5 years.

The end of study ("study completion") is defined as the date of the last protocol-specified visit/assessment (including telephone contact) for the last subject in the Long-Term Follow-Up Period.

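### Long-term deaths and secondary malignancies are summarised only as crude percentages of subjects who entered long-term follow-up, with no stated arm split, no use of follow-up time and no summary from randomisation

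*SAP*

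**What the plan says.** SAP 9.4.5 plans the number and percentage of subjects with a secondary malignancy and the number and percentage of deaths during LTFU, with cause if known. Both "will be tabulated for all subjects who participated in the LTFU period". The section names no treatment columns, no follow-up time and no time-to-event method. It does summarise how many subjects entered, "completed (Yes vs No), and remain ongoing during the 5-year LTFU period will be summarized", and adds: "The reasons for not entering the LTFU and the reasons for not completing the LTFU period will also be tabulated".

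SAP 4.1.1 defines LTFU as "Starting the day after the Follow-Up visit, up to and including a period of 5 years or death, whichever occurs first". When the Follow-Up visit falls depends on the OLE. Protocol 3.2 gives "Double-Blind Treatment Period and Observational Period of approximately 8 to 9 weeks" before it for subjects outside the OLE. OLE subjects continue until their chemotherapy regimen ends, and their visit is 30 days after the last dose (Protocol 3.1.4).

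Protocol 3.1.5 has subjects "contacted approximately every 6 months for up to 5 years by telephone", and records the date of death and the date of onset of any secondary malignancy.

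Deaths before LTFU appear as a row in the adverse event overview tables and in a death listing (SAP 9.2). Those tables cover the Double-Blind/Observational period, the OLE and the entire study. SAP 4.4 limits entire-study displays to subjects randomised to avatrombopag and defines no LTFU columns.

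**The concern.** Five years of telephone follow-up has one purpose: to learn about survival and secondary malignancy after a thrombopoietin receptor agonist in patients with active cancer. The natural questions are the risk from randomisation, or from first dose, and whether it looks similar in the two arms. The planned table answers neither.

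- **Denominator.** A subject who dies before the Follow-Up visit is in neither the numerator nor the denominator.
- **Clock.** Time zero moves with OLE participation, which is decided after randomisation.
- **Follow-up.** A subject with six months in LTFU carries the same weight as one with five years.
- **Arms.** No split is stated, and pre-LTFU and LTFU deaths are never added together by randomised arm.

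A reader of the long-term report could take the percentage as the risk in the trial population. If the table is produced by arm, the reader could take a difference in follow-up for a difference in risk.

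**Working it through.** SAP 9.4.5 states no figure to reproduce, and the documents give no mortality, malignancy or OLE-uptake rates. The inputs below are assumptions and the results are illustrations.

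**Assumptions.** Exponential survival with a 12-month median, the same in both arms: S(t) = 2^(−t/12), t in months. LTFU starts at 9 weeks without the OLE (upper end of Protocol 3.2) and at 30 weeks with it (assumed). In months: 9 × 7 / 30.44 = 2.07 and 30 × 7 / 30.44 = 6.90.

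**1. Deaths before LTFU.**
- S(2.07) = 0.887, so 11.3% die before LTFU without the OLE.
- S(6.90) = 0.671, so 32.9% die before LTFU with it.
- S(24) = 0.25, so the true 24-month risk from randomisation is 75% in both arms.

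**2. Crude LTFU death percentage at 24 months from randomisation.** With OLE uptake u:

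crude(u) = [u(0.671 − 0.25) + (1 − u)(0.887 − 0.25)] / [0.671u + 0.887(1 − u)]

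| OLE uptake, avatrombopag vs placebo | Crude, avatrombopag | Crude, placebo | False gap |
|---|---|---|---|
| Equal (50% each shown) | 67.9% | 67.9% | 0 points |
| 60% vs 40% | 67.0% | 68.8% | 1.8 points |
| 100% vs 0% | 62.8% | 71.8% | 9.0 points |

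Every crude figure is below 75%, including the row with no gap. If uptake were higher on placebo, the sign of the gap would reverse. Once every subject's five-year window is complete, the crude figure is 1 − 2^(−60/12) = 96.9% in both arms at any uptake, and the gap is zero.

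**3. Selection alone.** Assume 60% mortality from randomisation in both arms and a share e dead before LTFU. The LTFU percentage is (0.60 − e)/(1 − e).
- e = 10% in both arms: 55.6% and 55.6%.
- e = 5% vs 15%: 57.9% vs 52.9%.
- e = 10% vs 20%: 55.6% vs 50.0%, a false gap of 5.6 points.

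**4. Incomplete follow-up alone.** With follow-up spread evenly over 0 to 2 years and the same 12-month median, the crude death percentage is 1 − (1 − 0.25)/(2 ln 2) = 46%, against a two-year risk of 75%. This shortfall is the same in both arms.

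**5. Secondary malignancy.** Assume 2 per 100 person-years in everyone and ignore death. Then 1 − exp(−0.02 × years) gives 5.8% at 3.0 years, 4.9% at 2.5, 3.9% at 2.0 and 2.0% at 1.0. The rate is constant; only the follow-up changes.

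**6. Precision.** Mean survival is 12/ln 2 = 17.3 months, or 1.44 years. The 40 planned placebo subjects would give about 40 × 1.44 = 58 person-years and 58 × 0.02 = about one malignancy.

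**The case against.** The best defence is that the table is descriptive and partly supported elsewhere. Much of that stands.

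- A reader might infer that the plan compares the arms on a selected group. SAP 9.4.5 states no arm split, test or contrast, so the documents do not support this. The missing split is itself a gap, though table layouts sit in a separate document (SAP 11) and may include arm columns.
- A reader might infer that everyone who stopped early is dropped. Protocol 4.5 keeps all subjects in LTFU unless consent is withdrawn, and Protocol 4.5.1 follows those who only stop study drug. The subjects who fall out are those who die, withdraw consent or are lost before LTFU.
- A reader might take the 9-point gap as the expected bias. It needs every avatrombopag subject and no placebo subject to enter the OLE. The OLE is offered to both arms, and uptake is not given. Uptake could differ, since entry requires staying on the same chemotherapy agents (Protocol 4.3), but that is a possibility only.
- Entry, completion, ongoing status and reasons are tabulated, and earlier deaths are tabulated by period and listed. This makes the selection visible but does not correct the percentage.
- Survival and secondary malignancy are not efficacy endpoints, and LTFU data are reported after the final analysis (Protocol 10.2), so the trial's main conclusions are untouched. With about one expected placebo malignancy, and some placebo subjects taking open-label avatrombopag, any arm contrast would be weak.

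The metric itself remains undefended: SAP 9.4.5 is the only planned summary of these five-year data, and a descriptive percentage still needs an interpretable denominator and time frame.

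**Conclusion.** The point holds in limited form. SAP 9.4.5 gives crude percentages among LTFU participants, from a clock that starts at a variable time after randomisation, without follow-up time and without a stated arm split. No output described in the SAP combines earlier and later deaths by randomised arm. The figures therefore do not estimate risk from randomisation. While follow-up is incomplete they understate it: 63% to 72% against 75% at 24 months under the assumptions above, and 46% against 75% if follow-up is spread over 0 to 2 years.

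Distortion between arms is a risk that depends on OLE uptake or follow-up differing by arm. Under the same assumptions it runs from 0 points (equal uptake) through about 2 (60% vs 40%) to 9 (100% vs 0%, the extreme). The documents do not show that it will occur. Survival, malignancy rate, OLE length and uptake are all assumed. The primary endpoint and the sample size are unaffected. The change is worth making because the stated method can be replaced by a better one with dates already collected.

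**What to change.** In SAP 9.4.5:

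- Report all-cause death from randomisation in the FAS by randomised arm with Kaplan-Meier, censored at last contact, combining deaths before and during LTFU.
- Report secondary malignancy from first dose in the SAF by arm as events per 100 person-years. Take cases before LTFU from the adverse event data, because secondary malignancies are solicited as such only in LTFU. Cumulative incidence with death as a competing event is optional, given the few events expected.
- Show follow-up time by arm, and flag placebo subjects who received open-label avatrombopag.
- State the LTFU table columns, which SAP 4.4 leaves undefined.
- Keep the existing tables of entry, completion, ongoing status and reasons.

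The cost is SAP wording and a few standard descriptive outputs, with no new data collection. The estimates will be imprecise with about 40 placebo subjects and are affected by crossover to open-label treatment; the SAP should say so and plan no formal test.
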